The rationale for this study design is based on some of the feedback received from the VOICE and FEMPREP studies. Women in these studies reported high PrEP usage, remained in study and yet drug levels indicated very poor PrEP usage (Marazzo et al CROI 2013). Some rationale for this has been that PrEP acceptability was low, but with a keen perception among participants that study participation hinged on pill adherence. Thus, despite information that drug levels would be assessed, participants chose to report pill usage falsely. By making it very clear that trial participation does NOT hinge on PrEP usage (other than the first 3 months) we hope that we will get a more accurate assessment of real PrEP usage. We also hope that if participants really want to be taking PrEP, that adherence to product will persist. Other open label studies such as iPrEx OLE suggest this may be the case. By designing the study with an “opt out” arm we hope that we will create an authentic comparator group for participants taking oral PrEP (FTC/TDF) persistently and adherently, in order to assess any significant differences in adolescents taking oral PrEP (FTC/TDF) versus those who choose NOT to do so. We recognize that these may include demographic differences but may also include perceptions of risk, sexual activity, etc. In addition, we hope that this will give us a true sense of pill usage among this population- data that is currently unknown and required in order to more accurately model the impact of this intervention in this age group.

Both groups will be treated equally, except for administration of TDF/FTC therapy to those who select to include PrEP in their prevention package.

It was felt by the protocol team that the question of use and acceptability would best be answered by employing an open label design. The three month initial phase will mean that everyone will at least be exposed to 3 months of PrEP usage.

Adherence to medication can be measured in different ways depending on the condition and the

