7.8 LABORATORY EVALUATIONS AND PROCEDURES

Laboratory evaluations will include the following:

- Hepatitis B surface antigen and antibody testing
 - At Screening
- Urine pregnancy test
 - At every visit
- HIV serology
 - At every visit
- HSV-2 serology
 - At screening, Week 12, 48
- Chlamydia, and Gonorrhea.

- At screening, Week 12, 48
- Serum chemistries, creatinine only
 - Week 52
- AST, ALT
 - Screening, Week 12, 24, 36, 48 and 52
- Full Blood Count
 - Screening, Week 12, 24, 36, 48
- Haematocrit
 - Week 4, 8, 52
- DBS / Plasma drug level sampling
 - Week 4, 8, 12, 24,
 - Week 36, 48, for those who remain on study product
 - Week 52, Plasma only for those who remain on study product
- Urine dip stick
 - Screening, Week 12, 24, 36, 48

The location of laboratory evaluations will depend on laboratory capacity.

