7.12 BIOHAZARDOUS WASTE

The Principal Investigator will ensure that biohazardous waste will be contained according to institutional, transportation/carrier, and all applicable regulations.

Table1: Schedule of Study Visits and Procedures**Nb. Screening visit (up to -4 weeks); Enrollment (0 weeks); Final visit (52 weeks).**

Visit week	Prior	Screening	Enrolment	4	8	12	24	36	48	Final 52
Obtain written informed consent for screening and enrolment, from participant and his/her guardian		X								
Assessment of understanding for ICF		X								
Identification number assignment		X								
Locator information		X	X	X	X	X	X	X	X	X
HIV pre-and post-test counselling		X	X	X	X	X	X	X	X	X
Eligibility assessment (including review of all screening documentation)			X							
Sexual risk behavior questionnaire			X	X	X	X	X	X	X	X
Acceptability questionnaire				X	X	X	X	X	X	X
Adherence assessment and counselling				X	X	X	X	X	X	
Feedback of DBS or plasma results to those who agree to this.				X	X	X	X*	X*	X*	
Provision of condoms, condom counselling and rest of prevention package (bar PrEP)		X	X	X	X	X	X	X	X	X
Study product supplies and instructions *Only to those who indicate willingness to use.			X	X	X	X*	X*	X*		

Visit week	Prior	Screening	Enrolment	4	8	12	24	36	48	Final 52
Reimbursement	X	X	X	X	X	X	X	X	X	X
Schedule next visit (if applicable)		X	X	X	X	X	X	X	X	*
Focus group (including assent/consent)	X									X
Obtain/update medical history		X	X	X	X	X	X	X	X	X
Conduct physical exam		X	*	*	*	*	*	*	X	*
Incl TS at enrollment and week 48										
Disclose available test results		X	X	X	X	X	X	X	X	X
Provide or refer for contraception		X	X	X	X	X	X	X	X	*
Contraceptive counseling		X	X	X	X	X	X	X	X	X
Record/update AEs including social harms/benefits			X	X	X	X	X	X	X	X
Treat or prescribe treatment		*	*	*	*	*	*	*	*	*
Syndromic treatment for STIs										
Hepatitis B sAb/sAg testing		X								
Hepatitis B vaccination		*	*				*			
HIV serology		X	X	X	X	X	X	X	X	X
Herpes (HSV-2)		X				X			X	
Chlamydia, and Gonorrhea testing.										
Females low vaginal self-swab		X				X			X	
Males Urine										
Serum chemistries		X				X	X	X	X	
Creatinine Clearance										X
ALT/AST serology		X				X	X	X	X	X
Haematocrit				X	X					X
Full Blood count		X				X	X	X	X	
Measurement of study drug levels (DBS and plasma for drug levels)				X	X	X	X #	X #	X #	X #
Measurement of study drug levels by DBS only										X #

Visit week	Prior	Screening	Enrolment	4	8	12	24	36	48	Final 52

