 - Proportion of doses that are taken as instructed.

Sexual behaviour

- Reported number of steady and casual sex partners, condom use (and change after introduction of study product), substance use prior to or during sex, as evidenced by participant responses to interviewer-administered questionnaires and focus group.
- Proportion of scheduled HIV testing appointments that are missed, in relation to individual characteristics (age, sex, number of partners, use of other prevention methods) and the characteristics of the product.

Consistent with the exploratory objective to assess the HIV incidence in study participants during the course of study participation, the following endpoint will be assessed:

- HIV infection, as measured by seroconversion of study participants during the approximate 12 months of follow-up

Exploratory Endpoints:

- Consistent with the exploratory study objective to explore the feasibility of biofeedback of Blood Spot results as an adherence enhancing strategy in 150

CHAMPS: Choices For Adolescent Prevention Methods for SOUTH AFRICA

Pilot study B: “PlusPills”

A Demonstration Open Label Study to Assess the Acceptability and Use of Truvada Pre-exposure Prophylaxis in Healthy, HIV-Uninfected Adolescents, 15-19 Years of Age.

HIV-negative adolescents, ages 15-19 years, the following exploratory endpoints will be assessed:

- Proportion and number of participants who are tested using DBS and received results of DBS compared to participants who are tested using DBS but do not receive biofeedback of results.
- Number of counselling opportunities in which drug level feedback is requested vs total number of counseling events
- Number and nature of participants who request drug level feedback .
- Correlation between self reported adherence and drug levels at each visit for each participant
- Correlation between self reported adherence and drug levels at each visit in the study overall.
- Proportion and number of participants whose adherence to study product improves when receiving the results of DBS compared to those who do not receive feedback of results as measured by endpoints above.

Consistent with the exploratory study objective to investigate the relationship between daily PrEP usage and sexual practices and behavior in adolescents, the following exploratory endpoints will be assessed

Sexual behaviour data obtained using questionnaires and a focus group.

STUDY HYPOTHESIS

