participant. In analysis, we will first use graphical approaches to display the proportions of participants reporting binary sexual risk behaviours (or means of continuous measures) at each study visit over the 12-month period. Following this, we will use repeated measures methods (as described above) for both binary and continuous dependent variables, with PrEP access treated as a binary variable distinguishing visits in on vs. off PrEP phases; in the first instance, these models will not include other covariates.

2b. Proportion of scheduled HIV testing appointments that are missed, in relation to individual characteristics (age, sex, number of partners, use of other prevention methods) and the characteristics of the product.

Analysis:

“Missed appointments” will be defined as participants being >7 days late for a visit scheduled on a 28-day cycle. This measure will be analysed as a binary variable following the repeated measures approaches described above.

3. Secondary: HIV Incidence

HIV infection, as measured by seroconversion of study participants during the approximate 12 months of follow-up

Analysis:

The incidence of HIV will be described using person-time (rates per 100 person years of observation) and product-limit (survival proportion) approaches. For both methods, the date of seroconversion will be the midpoint of the interval between the last negative and first positive HIV test. For participants lost to follow-up, the date of censoring will be one day after the last visit attended.

C. Exploratory Endpoints:

1. Exploratory: Dried Blood Spot/plasma biofeedback

Correlation of self reported adherence and presence of drug levels in participants who are tested using plasma drug levels or DBS and received results compared to participants who are tested using plasma/DBS but do not receive biofeedback of results.

CHAMPS: Choices For Adolescent Prevention Methods for SOUTH AFRICA

Pilot study B: “PlusPills”

A Demonstration Open Label Study to Assess the Acceptability and Use of Truvada Pre-exposure Prophylaxis in Healthy, HIV-Uninfected Adolescents, 15-19 Years of Age.

Analysis:

These data will be described as proportions at each study visit; while we will calculate differences in proportions attending between participant who do and do not receive biofeedback results, no formal statistical tests will be used for this exploratory endpoint.

2.Exploratory: Sexual behaviour by coital diaries

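### The per-participant correlation of self-report with drug level has at most 6 pairs per person, and SAP C.1 describes proportions instead of analysing either correlation endpoint

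*SAP*

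**What the plan says.** The exploratory biofeedback endpoints, repeated in the Protocol Summary, 4.2, 10.2 and the SAP, include two correlations. One is "Correlation between self reported adherence and drug levels at each visit for each participant". The other is "Correlation between self reported adherence and drug levels at each visit in the study overall". Neither comes with a coefficient, a unit of analysis or a minimum number of pairs.

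The only analysis text for the group is item C.1 of the SAP's Data Analysis Plan (the same text is in Protocol 10.6). It opens with "Correlation of self reported adherence and presence of drug levels in participants who are tested using plasma drug levels or DBS and received results", set against participants who were tested but received no feedback. The method that follows is different: "These data will be described as proportions at each study visit". It then plans a difference in attendance proportions between participants who do and do not receive feedback, and adds that "no formal statistical tests will be used for this exploratory endpoint".

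The schedule limits the data. In Table 1 of the Protocol, the row "Adherence assessment and counselling" is marked at weeks 4, 8, 12, 24, 36 and 48, and not at week 52. Drug levels are taken at the same six visits and at week 52. Table 1 restricts the samples from week 24 onward to those on PrEP, and 7.8 has "Week 36, 48, for those who remain on study product".

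**The concern.** Two things do not fit. First, an index of both visit and participant leaves a single pair of values in each cell. If the intention is a correlation over one participant's visits, the number of pairs is very small. Second, the endpoints ask for correlations, while the analysis text describes proportions and compares attendance, which belongs to neither endpoint. An analyst would have to choose the method after seeing the data.

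The comparison has a purpose. Protocol 2.5 recalls earlier trials in which, on one explanation, "participants chose to report pill usage falsely". Protocol 2.6.7, under Non-Adherence, says that self-report over-states adherence. SAP A.1 also defines remaining on PrEP by self-reported use, so how well self-report matches drug levels affects how that result is read. A statistic that is undefined for constant reporters, and silent on the direction of error, serves this purpose poorly.

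**Working it through.** The plan states no figure for this endpoint, so there is none to reproduce. The check counts pairs from the schedule and asks what a coefficient can tell.

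**1. Literal reading.** One participant at one visit gives n = 1 and n - 2 = -1 degrees of freedom. The correlation is undefined.

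**2. Within participant, across visits.** A pair needs both an adherence assessment and a drug level. Table 1 has both at weeks 4, 8, 12, 24, 36 and 48. The week-52 drug level has no matching assessment, so the maximum is 6 pairs. Protocol 7.8 lists the week-24 sample without the on-product condition, but 7.4 limits the adherence assessment to those on product. A week-12 stopper who does not restart therefore has 3 pairs.

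The Fisher interval is tanh(atanh(r) ± 1.96/√(n - 3)). For r = 0.5, atanh(r) = 0.549. With n = 6 the half-width is 1.96/√3 = 1.132, so the limits are tanh(-0.582) = -0.52 and tanh(1.681) = 0.93.

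| PrEP stopped at (no restart) | Pairs | 95% CI at r = 0.5 |
|---|---|---|
| not stopped | 6 | -0.52 to 0.93 |
| week 36 | 5 | -0.68 to 0.96 |
| week 24 | 4 | -0.89 to 0.99 |
| week 12 | 3 | does not exist (n - 3 = 0) |

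If all of a participant's reports are equal, their variance is zero and r is undefined for any number of pairs. This applies to someone who reports perfect use every time.

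**3. Across participants at one visit.** This is computable. For illustration, r = 0.5 has a 95% CI of 0.36 to 0.62 with n = 135 and 0.34 to 0.63 with n = 100.

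**4. Size of over-reporting (illustrative series).** Take true adherence of 20, 40, 50, 60, 30 and 45%, with drug levels of 160, 250, 360, 460, 200 and 320 in arbitrary units.

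- Honest reports (mean 41%): Pearson 0.979, Spearman 1.000.
- Every report 30 points too high (mean 71%): Pearson 0.979, Spearman 1.000.
- Reports of 0.5 + 0.5x (mean 70%): Pearson 0.979, Spearman 1.000.

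**5. Direction of disagreement (illustrative tables, n = 135).**

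| | Reports use, drug detected | Reports use, none detected | Reports no use, drug detected | Reports no use, none detected |
|---|---|---|---|---|
| A | 60 | 40 | 5 | 30 |
| B | 60 | 5 | 40 | 30 |

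In both tables phi = (60×30 - 40×5)/√(100×35×65×70) = 1600/3991 = 0.401. Self-reported users without detectable drug are 40/100 = 40.0% in A (exact 95% CI 30.3 to 50.3%) and 5/65 = 7.7% in B (2.5 to 17.0%). The proportion separates the two tables, and phi does not.

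**6. Endpoint against analysis.** The endpoints need a coefficient, or a paired comparison of report with drug level. C.1 supplies proportions whose numerator and denominator are not given, and a difference in attendance. Neither correlation endpoint receives an analysis.

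**The case against.** The strongest case against is that this is loose wording in an exploratory endpoint with no planned test. The companion bullet contrasts each participant with the study overall, so the natural reading is within participant across visits, and that can be computed for many participants. Intervals for r also criticise an inference nobody plans. Much of this stands. The intervals are used here only to show how little a coefficient from 3 to 6 pairs conveys, even as description.

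A coefficient is not blind to every form of over-reporting. Suppose 65 of 135 have detectable drug and all of them report use. If none of the other 70 report use, phi = 1.00. If 40 of them do, phi = (65×30)/√(105×30×65×70) = 1950/3786 = 0.52. Selective over-reporting therefore lowers the coefficient. This stands too, but a low value still does not say which way the disagreement runs, as step 5 shows. The uniform 30-point shift is also a stylised case: it cannot happen above 70% true adherence if reports stop at 100%.

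Other parts of the plan help. SAP B.1 applies an effective-adherence category to both self-report and drug level at each visit, so a gap between the two cohort proportions would be visible. It is a comparison of totals, however, in which errors in opposite directions cancel. B.1 also lists a proportion linking detectable drug with reported use, but its denominator is ambiguous. If the denominator is those with detectable drug, over-reporters without drug are excluded. As for repeated samples, the study-wide correlation at each visit uses one sample per person, and B.1 already gives mixed models for repeated adherence measures. Only a summary pooled over visits needs a further rule.

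**Conclusion.** The point holds in a limited form. The per-participant correlation is undefined on its literal wording. On the natural reading it rests on 3 to 6 pairs for participants who attend every visit up to the time they stop and do not restart. It does not exist for constant reporters. The study-wide correlation is computable but does not measure the size or direction of over-reporting. C.1 carries out neither and compares attendance instead.

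The pair counts come from Table 1 and 7.4. The intervals assume the Fisher approximation. The series and the 2×2 tables are illustrations, because the documents give no rates.

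A reader might infer more than the documents support:

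- That nothing in this group can be computed, or that no workable reading could show over-reporting. A defined proportion of reported users without detectable drug would show it, and C.1 points towards proportions without defining that one.
- That the design rests on detecting false reports. Protocol 2.5 aims instead to remove the incentive, by making participation independent of PrEP use after the first 3 months.
- That each participant has 7 pairs. Seven is the number of drug samples.
- That a known share of participants would have no coefficient. Assuming 80% to 90% of visits are reported as perfect gives p^6 + (1 - p)^6 = 26% to 53%. But that rate is not in the documents, and the formula needs independent visits and a yes/no answer, whereas adherence is also graded on a visual scale.

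**What to change.** Keep the analysis exploratory and descriptive.

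- **Per participant:** replace the correlation with the number and proportion of that participant's sampled visits at which self-report and drug level disagree, split by direction (use reported without detectable drug; no use reported with detectable drug). State the number of sampled visits, since sampling from week 24 is limited to those on PrEP and the second direction will be seen less often.
- **At each visit, across participants:** report the proportion of self-reported users without detectable drug, with an exact 95% CI. A rank correlation may be added as description.
- **Pooled over visits:** allow for repeated samples from the same participant, by a participant random intercept or a bootstrap that resamples participants.
- **C.1:** replace the attendance comparison with these measures, by feedback received or not. Take feedback status visit by visit, because Protocol 6.4 lets participants choose differently each time.

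Make the same change in the Protocol Summary, 4.2, 10.2, the C.1 text in 10.6, and the SAP. The cost is a wording amendment. The self-reports and drug levels are already scheduled, so no new data are needed.

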6.5 CONCOMITANT MEDICATIONS AND PROCEDURES

With the exception of medications listed as prohibited (see below, this section), enrolled study participants may use concomitant medications during study participation. All concomitant medications, including prescribed and over-the-counter Preparations, vitamins and nutritional supplements, recreational drugs, and herbal Preparations reported within the 70 days prior to study enrollment and throughout the course of the study will be recorded on the Case Report

Forms (CRF) designated for that purpose. Medications used for the treatment of AEs that occur during study participation also will be recorded on applicable study case report forms.

Should participants report use of any of the following medications, they will be required to discontinue use of study drug: interleukin therapy, medications with significant nephrotoxic potential (including but not limited to amphotericin B, aminoglycosides, cidofovir, foscarnet and systemic chemotherapy), and medications that may inhibit or compete for elimination via active renal tubular secretion (including but not limited to probenecid). In addition, if a participant requests post-exposure prophylaxis (PEP) for HIV exposure, they will be referred to a health care provider for evaluation. If a participant starts ARV therapy for PEP, they should hold study medications until completion of the course of PEP.

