7.10.2 Participants Who Become Pregnant

If a female participant becomes pregnant after enrolment into the study, the study product will be immediately terminated, the protocol-specified visit schedule will be followed (for participants who choose to be maintained in follow-up), and the participant will be followed until delivery. The participant will be counseled about available options and appropriate referrals will be made depending on the participants' choice. Participants will also be encouraged to disclose their pregnancy results to a trusted adult (not necessarily the parent/ guardian) [See Section 9.3 for more details].

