9.7 CRITERIA FOR DISCONTINUATION

The criteria for permanent discontinuation of further study product for an individual participant are:

- Product-related toxicity (see Section 9.1)
- Requirement for prohibited concomitant medications
- HIV infection
- Pregnancy/lactation
- Completion of study as defined in the protocol
- Request by participant to terminate study product
- Any conditions or clinical reasons that will threaten safety and well-being of participant

The criteria for premature discontinuation of further study participation for an individual participant are:

- Lost to follow up as per site SOP
- Participant repeatedly non-compliant with study product as prescribed
- Pregnancy/lactation
- Request by participant to withdraw from study
- Request of the primary guardian or caregiver if s/he thinks the study is no longer in the best interest of the participant
- Participant judged by the Site Investigator to be at significant risk of failing to comply with the provisions of the protocol as to cause harm to self or seriously interfere with the validity of study results
- At the discretion of the Independent Ethics Committee, Medicine Control Council, Site Investigator, or pharmaceutical supporter.
- DAIDS, NIAID, the Office of Human Research Protection (OHRP), and the FDA as regulatory entities may also discontinue the study at their discretion.

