The DTHF protocol and research teams hypothesize that oral once daily PrEP (TDF/FTC) will be acceptable and utilized safely by healthy adolescents, between the ages of 15-19 years.

SAMPLE SIZE CONSIDERATIONS

The sample size calculation is based on the ability to detect the measure the primary

CHAMPS: Choices For Adolescent Prevention Methods for SOUTH AFRICA

Pilot study B: “PlusPills”

A Demonstration Open Label Study to Assess the Acceptability and Use of Truvada Pre-exposure Prophylaxis in Healthy, HIV-Uninfected Adolescents, 15-19 Years of Age.

objectives (acceptability and use) in the participant population. The table below shows the precision (as 95% confidence limits) provided by various sample sizes in detecting the occurrence of acceptability endpoints (with a frequency non- uptake and use varying from 5%-20%).

Acceptability will be measured by proportion of youth who take up PrEP and remain on PrEP as part of a comprehensive prevention package. Also they will complete an acceptability questionnaire.

	Precision *		
Frequency	n=100	n=135	n=170
5%	1.6; 11.2	2.1; 10.4	2.4; 9.8
10%	4.9; 17.6	5.7; 16.8	6.4; 16.2
15%	8.6; 23.5	9.9; 22.8	10.7; 22.2
20%	12.7; 29.1	14.2; 28.6	15.3; 28.1

* Asymptotic (exact) binomial 95% confidence limits

Based on these calculations, we anticipate that 135 participants, rounded up to 150 participants to account for premature censoring (due to loss to follow-up and/or withdrawal of consent, estimated at maximum 10%) will be required to detect non-acceptability endpoints that occur in 10% of subjects with approximately 5% precision.

DATA AND SAFETY MONITORING AND REVIEW

In addition to the informal safety monitoring done by the Site Investigator and study clinician, DTHF will convene an independent Protocol Safety Review Team (PSRT). The roles of the PSRT are:

CHAMPS: Choices For Adolescent Prevention Methods for SOUTH AFRICA

Pilot study B: “PlusPills”

A Demonstration Open Label Study to Assess the Acceptability and Use of Truvada Pre-exposure Prophylaxis in Healthy, HIV-Uninfected Adolescents, 15-19 Years of Age.

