participants. Should the SMC or the PSRT detect evidence of harm such that the recommendation for halting or modifying the study is made, then this will be communicated to the PI, The protocol team and the DAIDS prevention division. The IRB and MCC will also be informed of the discontinuation of the study and/or the modification and reasons for modification of the study. All further enrollment, and study activities other than safety follow up will be put on hold. Participants, guardians and CABS will be notified as soon as possible after next steps are identified.

DATA ANALYSIS PLAN

A customized data entry and management system will be implemented for the project in Microsoft Access. Data will be analysed using the statistical programme STATA (Stata Corporation, College Station, Texas, USA). Simple descriptive statistics including frequency distributions will be used to assist in data cleaning and summarization.

The analysis plan for each of the study objectives (per 10.2 above) is detailed below. (Note that throughout the analysis, all statistical tests will be 2-sided using an alpha of 0.05.)

Endpoints:

A. PRIMARY

1. Primary: Use

Number of adolescents who continue to use PrEP after the initial 3 month period and the total time on PrEP for each adolescent and for the cohort as a whole.

Analysis:

Proportions of participants (a) willing to use and (b) taking up PrEP will be described with point estimates and exact 95% confidence intervals. “Remaining on PrEP” will be defined as any self-reported use of PrEP at each study interval (regardless of adherence) over the 9-month follow-up period, as a binary outcome. The first 3-month “use” will be 100% for all 150 participants. We will use product-limit methods to examine ‘survival’ proportions for

CHAMPS: Choices For Adolescent Prevention Methods for SOUTH AFRICA

Pilot study B: “PlusPills”

A Demonstration Open Label Study to Assess the Acceptability and Use of Truvada Pre-exposure Prophylaxis in Healthy, HIV-Uninfected Adolescents, 15-19 Years of Age.

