participants remaining on PrEP, accounting for censoring due to loss to follow-up. We will (i) examine the reasons for discontinuation and (ii) examine the baseline and/or pre-LTF characteristics of those LTF, and compare to those retained, in order to understand the possible associations between LTF and adherence and/or sexual risk taking. While our preliminary analyses will presume this censoring is uninformative, we will include analyses that assume LTF are non-adherent. Our intention is to (i) examine the reasons for discontinuation and (ii) examine the baseline and/or pre-LTF characteristics of those LTF, and compare to those retained, in order to understand the possible associations between LTF and adherence and/or sexual risk taking. While our preliminary analyses will presume this censoring is uninformative, we will include analyses that assume LTF are non-adherent. In subsidiary analyses for this primary endpoint, we will also examine the factors associated with PrEP willingness, uptake and “remaining on PrEP” using standard methods (including chi-square and exact tests for the comparisons of proportions, and log-rank tests for the comparison of ‘survival’ curves in product-limit analysis).

2. Primary: Acceptability

An acceptability questionnaire will be administered 3 monthly to assess reasons for continuing, stopping or restarting PrEP. A further questionnaire will be administered at the final study visit to assess the delivery of PrEP and the content of the study visits, including the user-friendliness of the medication regimen (including an assessment of side effects), the delivery format, the dosing strategy, and the clinic visit schedule.

Analysis Plan:

This acceptability questionnaire will contain both binary items as well as continuous (interval) measures from Likert-type items. Analysis of data from this questionnaire will begin with standard descriptive statistics for each item, overall and by key participant subgroups (a priori, these will be based on participant age, gender, sexual activity during the study and PrEP adherence during the study). We will compare responses to acceptability items using standard methods, including chi-square and exact tests; Student’s t- and rank-

CHAMPS: Choices For Adolescent Prevention Methods for SOUTH AFRICA

Pilot study B: “PlusPills”

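### The acceptability proportion counts participants whom the protocol takes off PrEP as not remaining on PrEP, together with those who chose to stop

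*SAP*

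**What the plan says.** **Measure.** SAP, Sample Size Considerations (same text in Protocol 10.4): "Acceptability will be measured by proportion of youth who take up PrEP and remain on PrEP as part of a comprehensive prevention package". The same section calls the complement non-acceptability and sizes the study to estimate it at 10% with about 5% precision.

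**Definition.** SAP A.1 (Protocol 10.6) defines remaining on PrEP as "any self-reported use of PrEP at each study interval (regardless of adherence) over the 9-month follow-up period, as a binary outcome". The product-limit analysis concerns "participants remaining on PrEP, accounting for censoring due to loss to follow-up". The plan will also "examine the reasons for discontinuation". No rule carries those reasons into the proportion or the curve.

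**Mandated stops.** Protocol 9.7 begins one list with "The criteria for permanent discontinuation of further study product for an individual participant are". It names product toxicity, prohibited medication, HIV infection and pregnancy or lactation, with the participant's own request as a separate item. On pregnancy, 7.10.2 says "the study product will be immediately terminated" and then continues the visit schedule for those who agree. Sections 7.10.1 (HIV infection) and 9.3 (pregnancy) also continue follow-up off product. The Protocol Summary follows everyone for 12 months whether or not they use PrEP.

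**Conflict.** A second list in 9.7 also makes pregnancy or lactation a criterion for leaving the study, which does not fit 7.10.2 and 9.3.

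**The concern.** Acceptability should show whether adolescents want PrEP and keep choosing it. After week 12 the protocol supplies product only to participants who want it and have no contraindication. Someone who is pregnant, has acquired HIV or needs a prohibited drug is no longer offered that choice, so her non-use is not a refusal. The protocol separates participant request from the other reasons for stopping; the endpoint merges them.

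Two things are at stake. The reported non-acceptability would mix refusal with withdrawal by rule, in unknown shares. And pregnancy stops can fall only on girls, so any comparison of remaining on PrEP by gender would be affected by the protocol's own rule.

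**Working it through.** **1. The plan's own figures.** Allowance for censoring: 135 / (1 − 0.10) = 150, as stated. It covers loss to follow-up and withdrawal of consent, not mandated stops. Exact (Clopper–Pearson) 95% limits at n = 135:

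- 14/135 = 10.4%: 5.79% to 16.79% (10% row of the plan: 5.7; 16.8)
- 21/135 = 15.6%: 9.89% to 22.79% (15% row: 9.9; 22.8)

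The table is reproduced apart from a difference of 0.1 point. The Wald interval for 10% of 135 (4.9% to 15.1%) does not match, so the limits are exact ones.

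**2. Applying the rule.** Take a participant permanently stopped in weeks 12–24 who stays in follow-up.

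- Weeks 12–24: she used PrEP before the stop, so she scores as remaining.
- Weeks 24–36: she has no product and reports no use. She is not lost to follow-up, so she is not censored. She scores as not remaining.

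No sentence states this outcome; it follows from the definition together with the single censoring reason. A hold shorter than an interval does not trigger it.

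**3. Effect per stop.** Each mandated stop that registers, in someone who had not already stopped by choice, adds 1/135 = 0.74 or 1/150 = 0.67 points. Seven add 7/135 = 5.2 or 7/150 = 4.7 points. At n = 135, 14 + 7 = 21 moves the result from the plan's 10% row to its 15% row.

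**4. Illustration.** The documents give no rate of mandated stops, so the first column is an assumption. n = 135; voluntary stopping is about 10% of those still permitted PrEP, rounded to whole persons; all mandated stops register.

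| Mandated stops | Non-acceptability as planned (exact 95% CI) | Voluntary stops among those still permitted (exact 95% CI) |
|---|---|---|
| 3 | 16/135 = 11.9% (6.9–18.5) | 13/132 = 9.8% (5.4–16.3) |
| 5 | 18/135 = 13.3% (8.1–20.3) | 13/130 = 10.0% (5.4–16.5) |
| 8 | 21/135 = 15.6% (9.9–22.8) | 13/127 = 10.2% (5.6–16.9) |
| 12 | 24/135 = 17.8% (11.7–25.3) | 12/123 = 9.8% (5.1–16.4) |
| 15 | 27/135 = 20.0% (13.6–27.7) | 12/120 = 10.0% (5.3–16.8) |

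**5. Timing.** Product is last supplied at week 36 (Protocol 7.4). A stop in weeks 36–48 has no later supplied interval in which to register. If stops were spread evenly over 48 weeks (assumption), 12/48 = 25% would never count, and seven registering stops would need about 7/0.75 = 9.3 in all.

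**6. Share of girls.** Protocol 4.1: 2 × 50 / 150 = 66.7%. Protocol 4.3: 2 × 45 / 150 = 60%.

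**The case against.** The strongest reply is that the plan already copes. Remaining on PrEP is analysed under Use, where an all-cause count is right. The separate Acceptability section relies on questionnaires, including a 3-monthly one on reasons for continuing, stopping or restarting. The study is single-arm and largely descriptive with no acceptability threshold, and reasons for stopping will be reported beside the estimate. The all-cause count for Use stands. But the sample size section and the endpoint list also make remaining on PrEP an acceptability measure, and neither the questionnaires nor a tabulation of reasons changes how that proportion is computed.

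A reader might go further than the documents allow in five ways.

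- *That a planned gender comparison would show girls finding PrEP less acceptable.* SAP A.1 speaks only of factors associated with remaining on PrEP. Gender is named as a subgroup for the questionnaire items and for adherence, not for this measure.
- *That mandated stops say nothing about acceptability.* This is too strong for toxicity, because the final questionnaire includes side effects.
- *That every pregnancy is scored as rejection.* Under 7.10.2 and 9.3 she is observed off product. Under the second list in 9.7 she leaves the study, and the SAP does not say how she is then analysed.
- *That the distortion is large.* A figure near 19%, such as (15 + 13)/150 = 18.7%, needs ten pregnancies and three other stops, all registering and none in someone who had already stopped. The documents give no such rates, and entry requires effective contraception and no intention of pregnancy (Protocol 5.2).
- *That participants who obey a hold fail the adherence measures.* A 14-day hold in 84 days gives 70/84 = 83%, and a 7-day hold in 28 days gives 21/28 = 75%, both under the 85% cut-off. That holds only if held days count as missed. The endpoint counts doses taken according to instruction, and for post-exposure prophylaxis the instruction is that "they should hold study medications until completion of the course of PEP" (Protocol 6.5). The pill-count example in SAP B.1 refers to daily dosing, so the text is ambiguous rather than wrong.

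**Conclusion.** The point holds in a limited form. By the stated rule, a participant permanently taken off product who stays in follow-up counts against acceptability from the first full interval without product. Neither document censors such stops, treats them as competing events or excludes them.

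The size cannot be fixed from the documents. It is about 0.7 points per registering stop, and about seven would equal the stated precision. With two or three stops, the shift lies well inside the planned interval. Stops late in follow-up and holds within an interval may not register at all. For pregnancy the conclusion also depends on how 9.7 is reconciled with 7.10.2 and 9.3. The sample size is unaffected. This is an inexpensive improvement to the meaning of a primary measure; it does not invalidate the study.

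**What to change.** 1. **SAP A.1.** Classify each discontinuation as voluntary or protocol-mandated (Protocol 6.5, 7.10, 9.1, 9.7) from the recorded reason.
2. **Acceptability.** Report the cumulative incidence of voluntary discontinuation, with permanent mandated stop as a competing event. Show toxicity stops on their own line, because tolerability is part of acceptability.
3. **Restarts.** State how they count: for example, time to first voluntary stop, plus interval-specific proportions among those still permitted PrEP.
4. **Use.** Keep all-cause remaining on PrEP.
5. **Pregnancy.** Reconcile the second list in Protocol 9.7 with 7.10.2 and 9.3, and state the analysis status of pregnant participants.
6. **SAP B.1.** State that the dose denominator follows the instruction given, so that documented instructed-hold days are not missed doses.

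**Cost.** SAP wording, one extra table, and two figures (voluntary and all-cause) where there was one. Reasons for participants' decisions (Protocol 7.4) and the action taken for adverse events (8.1) are already recorded. Neither section says that hold start and end dates are captured, so the case report form should be checked for item 6. Items 1 to 4 and 6 leave participant management unchanged; item 5 asks only that the sections agree.
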